13.4.7. Health Outcome Analyses

Health outcome endpoints are as follows:

- Durability in TSQM scores
- Durability in WPAI scores

- Durability in EQ-5D-5L scores

Summaries will be provided for the current study.

The between-treatment comparisons for combined analysis with Study BCX7353-302 for TSQM, WPAI, and EQ-5D-5L will be performed using a mixed effect model including terms of treatment, visit, visit interaction, and baseline score. Details will be provided in the SAP.

13.4.8. Pharmacokinetic Analyses

Plasma samples for determination of BCX7353 concentrations are planned to be collected per [Table 2](#) and [Table 3](#). Concentration data will be listed and summarized by treatment group for the current study alone.

The resulting PK data will then be pooled in a meta-analysis to facilitate population PK analyses. In the population PK analysis, covariates will be tested to determine the effect on PK of BCX7353. Region will be one of the covariates analyzed.

Pharmacokinetic results from the meta-analysis will not be summarized in the statistical reporting of this study.

13.4.9. Pharmacodynamic Analyses

Plasma kallikrein inhibition data will be expressed as percentage inhibition compared to subject baseline activity. Ex vivo plasma kallikrein activity will be listed by subject, treatment, day, and time, and summarized separately by treatment, day, and time. Using data from the current study alone, descriptive statistics will be reported. Mean and individual plasma kallikrein inhibition versus time profiles will be plotted by treatment group.

13.4.10. PK Concentration /Pharmacodynamic Analyses

This analysis of PK concentration-PD relationships may be performed using data from this study alone or may be combined with data from Study BCX7353-302. Exposure-response analyses of the relationships between plasma kallikrein inhibition, efficacy endpoints, and BCX7353 plasma concentrations may be explored using model-based techniques as applicable.

14. STUDY ADMINISTRATION

14.1. Regulatory and Ethical Considerations

14.1.1. Regulatory Authority Approvals

This study will be conducted in compliance with the protocol; GCPs, including ICH of Technical Requirements for Registration of Pharmaceuticals for Human Use Guidelines (ICH E6); Japan PMDA regulatory requirements and other national laws as applicable; and in accordance with the ethical principles of the Declaration of Helsinki. In addition, the study will be conducted in compliance with all applicable local laws and regulatory requirements relevant to the use of new therapeutic agents.

Following marketing authorization in Japan and formal transition to a post-marketing study, this study will be conducted in compliance with post-marketing regulations. The sponsor of the study

will be changed from BioCryst to the marketing authorization holder in Japan, OrphanPacific, Inc. However, the clinical conduct of the study will continue to be overseen by BioCryst. Therefore, reference to “the sponsor” in this section may encompass reference to BioCryst and/or OrphanPacific, Inc., as applicable.

14.1.2. Institutional Review Board and Ethics Committee Approvals

Before initiation of the study at an investigational site, the protocol, the ICF, the subject information sheet (if applicable), and any other relevant study documentation will be submitted to the appropriate IRB/IEC. Written approval of the study must be obtained before the study center can be initiated or the IMP can be released to the investigator. Any necessary extensions or renewals of IRB/IEC approval must be obtained, in particular, for changes to the study such as modification of the protocol, the ICF, the written information provided to subjects, and/or other procedures.

The IRB/IEC will be promptly provided any new information that may adversely affect the safety of the subjects or the conduct of the study. On completion of the study, the IRB/IEC will be provided with a report of the outcome of the study.

Written reports of clinical study status will be submitted to the IRB/IEC annually or more frequently if requested by the IRB/IEC. A final study notification will also be forwarded to the IRB/IEC after the study is completed or in the event of premature termination of the study in accordance with the applicable regulations. The study will be considered completed once the last subject completes the last study visit. Copies of all contact with the IRB/IEC should be maintained in the study file. Copies of clinical study status reports (including termination) should be provided to the sponsor.

14.1.3. Subject Informed Consent: Adults

A signed ICF must be obtained from each subject prior to performing any study-related procedures. Each subject should be given both verbal and written information describing the nature and duration of the clinical study. The informed consent process should take place under conditions where the subject has adequate time to consider the risks and benefits associated with his/her participation in the study. Subjects will not be screened or treated until the subject has signed an approved ICF written in a language in which the subject is fluent.

The ICF that is used must be approved both by the sponsor and by the reviewing IRB/IEC. The ICF should be in accordance with the current revision of the Declaration of Helsinki, current ICH and GCP guidelines, and sponsor policies.

The investigator must explain to potential subjects the aims, methods, reasonably anticipated benefits, and potential hazards of the trial and any discomfort it may entail. Subjects will be informed that they are free not to participate in the trial and that they may withdraw consent to participate at any time. They will be told that refusal to participate in the study will not prejudice future treatment. They will also be told that their records may be examined by competent authorities and authorized persons, but that personal information will be treated as strictly confidential and will not be publicly available. Subjects must be given the opportunity to ask questions. After this explanation and before entry into the trial, consent should be appropriately recorded by means of the subject’s dated signature. The subject should receive a signed and dated copy of the ICF. The original signed ICF should be retained in the study files.

The investigator shall maintain a log of all subjects who sign the ICF and indicate if the subject was enrolled into the study or reason for non-enrollment.

14.1.4. Subject Informed Consent: Adolescents

Signed informed consent must be obtained from each parent/caregiver of adolescent subjects aged 12 to 17 years who enroll in the study prior to performing any study-related procedures. Similarly, subject assent by subjects 12 to 17 years will be obtained from each adolescent prior to performing any study-related procedures. If the local requirements limit the age of assent, then assent will be obtained based on those requirements. Each parent/caregiver and subject should be given both verbal and written information describing the nature and duration of the clinical study. The informed consent process should take place under conditions where the parent/caregiver has adequate time to consider the risks and benefits associated with his/her child's participation in the study. Subjects will not be screened or treated until the parent/caregiver and subject have signed an approved ICF and assent form written in a language in which the subject is fluent. The ICF and assent forms that are used must be approved both by the sponsor and by the reviewing IRB/IEC. The ICF and assent forms should be in accordance with the current revision of the Declaration of Helsinki, current ICH and GCP guidelines, and sponsor policies.

The investigator must explain to potential subjects and their parent/caregiver the aims, methods, reasonably anticipated benefits, and potential hazards of the trial and any discomfort it may entail. Each parent/caregiver will be informed that they are free for their child not to participate in the trial and that they may withdraw consent for their child to participate at any time. They will be told that refusal for their child to participate in the study will not prejudice future treatment. They will also be told that their child's records may be examined by competent authorities and authorized persons, but that personal information will be treated as strictly confidential and will not be publicly available.

Parents/caregivers and subjects must be given the opportunity to ask questions. After this explanation and before entry into the trial, consent and assent should be appropriately recorded by means of the parent's/caregiver's dated signature. The parent/caregiver should receive a signed and dated copy of the ICF, and the assent. The original signed informed consent and assent should be retained in the study files. The investigator shall maintain a log of all subjects for whom consent was signed and indicate if the subject was enrolled into the study or reason for non-enrollment.

14.1.5. Investigator Reporting Requirements

The investigator will provide timely reports regarding safety to his/her IRB/IEC as required.

14.2. Study Monitoring

During trial conduct, the sponsor or its designee will conduct periodic monitoring visits to ensure that the protocol and GCPs are being followed. The monitors will review source documents to confirm that the data recorded in the eCRFs are accurate. The investigator and institution will allow sponsor representatives, monitors, or its designees direct access to source documents to perform this verification.

It is important that the principal investigator(s) and their relevant personnel are available during the monitoring visits and that sufficient time is devoted to the process.

14.3. Quality Assurance

The principal investigator may be subject to visits by the IRB/IEC, and/or by a quality assurance group for audits performed by the sponsor or its designee, and/or to inspection by appropriate regulatory authorities.

It is important that the investigator(s) and their relevant personnel are available during the possible audits or inspections and that sufficient time is devoted to the process.

14.4. Study Termination and Site Closure

Overall, the sponsor may suspend enrollment into the study, suspend treatment of ongoing subjects, or terminate the study to ensure that subjects' safety and welfare are protected.

The entire study, or individual sites, may be terminated for any of the following reasons:

- if the study drug becomes commercially available or another mechanism is available to provide drug to the subject
- changes in scientific knowledge that lead to a negative impact on the benefit-risk profile for subjects
- request of sponsor or competent public authorities/IRB/IEC
- if recruitment cannot be completed in specified time frame
- if the permit to manufacture or import IMP is revoked

The sponsor reserves the right to discontinue the trial prior to inclusion of the intended number of subjects but intends only to exercise this right for valid scientific or administrative reasons. After such a decision, the investigator must contact all participating subjects immediately after notification. As directed by the sponsor, all study materials must be collected and all eCRFs completed to the greatest extent possible.

An individual trial center that is determined to be unsuitable by the sponsor, competent public authorities, or IRB/IEC may be terminated, without affecting the other trial sites.

Except for those situations outlined in Section 8.3, no other formal stopping rules will be defined for individual subjects, parts of the trial, or the entire trial. Individual subjects will be discontinued from the study following the emergence of any laboratory abnormality or AE that in the judgment of the investigator compromises the ability to continue study-specific procedures or is considered not to be in the subject's best interest.

Once BCX7353 receives marketing authorization in Japan, this study will be transitioned to a post-marketing study. Each subject remaining on study may continue to receive access to BCX7353 via this study until such time as BCX7353 is commercially available at his or her study center. Once the last subject is able to access commercial drug product, the study will be terminated.

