8.3. Subject Withdrawal from the Study and from Study Drug

8.3.1. Subject Withdrawal from the Study

Participation in the study is strictly voluntary; a subject may withdraw consent to contribute additional study information at any point. A subject who withdraws consent will be requested to attend an early termination visit to complete all EOS evaluations. Although a subject may withdraw from the study at any time without specifying a reason for withdrawal, the reason for withdrawal, if provided by the subject, will be recorded in the subject's medical records (source documents) and also in the electronic case report form (eCRF). If the reason for subject withdrawal is not known, the subject must be contacted to establish whether the reason was an AE, and if so, this must be reported in accordance with the procedures outlined in Section 12. If at any point in the study the clinic is unable to contact the subject after appropriate attempts have been made, the subject will be considered lost to follow-up.

Once subjects have withdrawn from the study, the sponsor will no longer provide treatment through the study. Following withdrawal from the study, a subject will be able to receive further treatment as recommended by his or her treating physician and according to the accepted standard of care.

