8.3.2. Subject Discontinuation from Study Drug

A subject will be permanently discontinued from study drug for any of the following reasons, which will be recorded in the source documents and eCRF.

- Emergence of any laboratory abnormality or AE that in the judgment of the investigator compromises the ability of the subject to continue study-specific procedures or it is considered not to be in the subject's best interest due to an altered benefit-risk profile.
- Reoccurrence of treatment-emergent AST or ALT elevation $> 5 \times \text{ULN}$ (confirmed) if BCX7353 is restarted after meeting hold criteria as outlined in Section 12.2.2.
- Treatment-emergent ALT or AST $> 3 \times \text{ULN}$ combined with either laboratory abnormalities indicative of significant hepatic toxicity (ie, meeting Hy's law, total bilirubin $> 2 \times \text{ULN}$ OR with an international normalized ratio [INR] > 1.5) or with symptomatology of acute hepatitis (ie, severe fatigue, nausea, vomiting, right upper quadrant pain and tenderness, fever, rash, and/or eosinophilia [$> 5\%$]).
- Subsequent determination that inclusion/exclusion criteria were not met.
- Intercurrent illness or emergence of a new illness/medical condition that would, in the judgment of the investigator, affect assessments of clinical status to a significant degree.

- Subject noncompliance with study drug or to the protocol.
- The subject has a QTcF > 500 msec (confirmed on repeat ECG testing).
- The subject has a QTcF increase of more than 60 msec (confirmed by repeat ECG) from the mean QTcF value obtained from triplicate ECGs obtained at the baseline visit and a simultaneous absolute QTcF > 450 msec (male) or 470 msec (female).

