- Subjects with a study drug-related Grade 3 or 4 rash as described by the Division of Microbiology and Infectious Diseases (DMID) criteria “skin-mucocutaneous” will be discontinued from study drug and treated according to best medical practice. All subjects with a suspected drug rash should undergo specific rash evaluation as described in Section 12.2.1. A Grade 3 rash is defined as vesiculation or moist desquamation or ulceration and a Grade 4 rash is defined as exfoliative dermatitis, mucous membrane involvement or erythema multiforme or suspected Stevens-Johnson syndrome or necrosis requiring surgery. Subjects with a Grade 1 or 2 study drug-related rash may be continued on BCX7353 if the investigator, subject, and sponsor deem it appropriate. The protocol for continuing BCX7353 in the presence of a rash is described in Section 12.2.1.

Subjects who discontinue from study drug in Parts 1 or 2 will be requested to complete all regularly scheduled visits and procedures outlined in Table 2 and Table 3 through the end of the study part (ie, Part 1 or 2) in which they were currently being treated. Subjects who discontinue in Part 1 will be requested to complete all regularly scheduled visits and procedures through Week 24. Subjects who discontinue in Part 2 will be requested to complete all regularly scheduled visits and procedures through Week 52. Subjects who discontinue in Part 3 will have an EOS visit 3 weeks after the last dose of study drug. All subjects who discontinue from all parts should be treated in accordance with local clinical practice for HAE.

If a subject who discontinues from study drug subsequently withdraws consent to continue study visits as previously outlined, please see Section 8.3.1.

Subjects are not eligible for treatment in Parts 2 or 3 if they discontinue study drug in Parts 1 or 2, respectively due to any of the above cited reasons.

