10.3.5.3. Early Termination Visit/Follow-Up/End-of-Study

The following assessments will be performed for study completers at the EOS or at the Early Termination/Follow-Up visit (as applicable) for those subjects who discontinue, held approximately 3 weeks following the last dose of study drug.

Subjects who will transition to commercial drug product will have an EOS visit once BCX7353 is commercially available at each site. Subjects who transition to commercial BCX7353 will not need to return 3 weeks after their last dose of study drug. These assessments will also be conducted at an Early Termination Visit for those withdrawing consent (see Section 8.3.1):

- Subject weight
- Targeted physical examination

- Vital signs (blood pressure and pulse rate)
- 12-lead ECG
- Blood collection for clinical chemistry, hematology, coagulation, troponin I and troponin T, NGAL, and CK-MB
- Urine collection for urinalysis, possible reflex testing for abnormal GGT, and urine pregnancy test for all female subjects of childbearing potential
- Review of concomitant medications and AEs
- Review and collection of e-diary
- Blood for plasma PD and PK concentration analysis (early termination visit before Week 52 only)

If an AE is ongoing at the last follow-up visit, additional clinic visit(s) or telephone contact(s) may be warranted (see Section 12.1.2).

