11.3. Patient-Reported Outcomes

The AE-QoL, TSQM, and WPAI will each be administered once at baseline (pre-dose) and at Weeks 4, 8, 12, 18, 24, 28, 32, 36, 48, 52, 60, 72, 84, 96, and 104.

The EQ-5D-5L will be administered once at baseline (pre-dose) and at Weeks 4, 8, 12, 18, 24, 28, 32, 36, 48, 52, 60, 72, 84, 96, and 104. Subjects will fill out this questionnaire as instructed, describing their current health state today. During the on-treatment visits post-baseline, subjects will fill out a second EQ-5D-5L questionnaire if they have had an angioedema event since the previous visit. The subject will be instructed to fill out this second questionnaire based on a

recollection of his or her health state during an average angioedema event that they experienced since the previous visit.

Each questionnaire will be translated into Japanese. For all subject-completed forms, clinic staff should ensure the subject reads the instructions and completes the questionnaires in full prior to filling in the source documentation. For the baseline TSQM, separate guidance will be provided such that subjects complete their assessment with reference to their satisfaction with their usual standard of care treatment of HAE, prior to screening for the study.

Where possible, the questionnaires should be completed by the subject prior to other assessments for that visit to prevent influencing subject perceptions.

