Given that real-time access to e-diary entries for subjects is available via website access, the investigator (or designee) will proactively assess compliance, beginning during the screening period. Further training on completing the e-diary should be provided if e-diary completion compliance is < 90% at any point that during the study. A phone call may be necessary if compliance issues are noted in between clinic visits. Scheduled phone calls during the screening period and through Part 1 of the study to Week 24 are required to assess the subject's overall wellbeing, discuss compliance (if applicable), proper recording of angioedema event details (if applicable), or any usability issues with the e-diary.

Study staff are not permitted to make any entries into the e-diary and are not permitted to change entries.

In the event that a subject's e-diary becomes nonfunctional or is otherwise not available for data recording, a paper diary may be utilized for short-term angioedema event and dose recording until the subject receives a replacement e-diary. Other scenarios for which the use of the paper diary and/or the shipment of a replacement e-diary may be permitted, following consultation with the sponsor. During the period of paper diary use, it will be necessary for the subject to contact the investigator after each angioedema event that occurs.

Subjects who discontinue study drug should continue to record the occurrence of angioedema events in their e-diary until the follow-up visit.

11.4.1. Screening and Parts 1 and 2

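### Protocol 14.4 takes a subject out of the study for essentially the AE or laboratory trigger that 8.3.2 treats as a stop of study drug only

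*Protocol*

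**What the plan says.** Protocol 14.4 (Study Termination and Site Closure) ends its general text with two sentences that matter here. The first reads "Except for those situations outlined in Section 8.3, no other formal stopping rules will be defined for individual subjects", and extends this to parts of the trial and the trial as a whole. The second reads "Individual subjects will be discontinued from the study following the emergence of any laboratory abnormality or AE" where the investigator judges that the event compromises study procedures or that continuing is not in the subject's best interest.

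Protocol 8.3 keeps two states apart:

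- 8.3.1 covers leaving the study. The subject decides: "a subject may withdraw consent to contribute additional study information at any point". Loss to follow-up is the other route.
- 8.3.2 covers permanent discontinuation of study drug. Its first listed reason begins "Emergence of any laboratory abnormality or AE that in the judgment of the investigator compromises the ability of the subject". It then says "Subjects who discontinue in Part 1 will be requested to complete all regularly scheduled visits and procedures through Week 24", with the same request through Week 52 for Part 2.

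On data collection, Protocol 11.3 states "The AE-QoL, TSQM, and WPAI will each be administered once at baseline (pre-dose) and at Weeks 4, 8, 12, 18, 24", followed by later scheduled visits. The early termination and follow-up list in Protocol 10.3.5.3 has no AE-QoL, nor does the follow-up/early termination column of SAP Table 5. SAP 6.5.5 and 7.1 define completion of Part 1 by the Week 24 visit, not by remaining on drug.

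**The concern.** Two sections attach different actions to practically one trigger. Under 8.3.2 the subject stops capsules and is asked to keep attending. Under 14.4 the subject leaves, and no further visits are described. Both are worded as what will happen.

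The distinction has consequences in the analysis plan. A Part 1 subject who is off drug but attends Week 24 supplies the AE-QoL change at Week 24, a secondary endpoint, and counts as a completer. A subject removed before that visit does neither. Whether the score exists, and who is in the completers population, could then depend on which section the site read.

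**Working it through.** The plan gives no figure on this point to reproduce. The check is a comparison of texts, followed by a rough count of subjects.

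**Comparison**

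| | Protocol 8.3.2 | Protocol 14.4 |
|---|---|---|
| Trigger | Investigator-judged AE or laboratory abnormality: procedures compromised, or not in the subject's best interest because benefit-risk has changed | The same two limbs, without the benefit-risk wording |
| Action | Permanent stop of study drug | Discontinued from the study |
| What follows | Visits requested through Week 24 or Week 52 | Nothing stated |

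The pointer to 8.3 does not reconcile these, because nothing in 8.3 has the investigator remove a subject from the study for an AE. The conflict is clearest for the best-interest limb. Where the AE itself prevents procedures, visits may be lost under either section. The ALT/AST, QTcF and rash rules in 8.3.2 are separate and concern drug only. In Part 3, 8.3.2 itself goes to an end-of-study visit 3 weeks after the last dose, so the two sections differ little there.

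**Effect on each analysis, if 14.4 is followed before Week 24**

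- Week 24 AE-QoL: lost, since the early termination visit does not collect it. SAP 8.7.1 uses a repeated-measures model, so AE-QoL from visits already made still contributes. One missing score is 1/8 = 12.5% of the Week 24 scores in an arm of this study, or 1/48 = 2.1% in the combined analysis (48 per group, SAP 4.3.2), where SAP 8.7 places this endpoint. These are shares of scores, not of information.
- Completers population: the subject drops out. This population serves only a sensitivity analysis of the primary endpoint (SAP 6.5.5, 8.6.2).
- Primary analysis: unaffected, because SAP 8.6.1 excludes data after treatment discontinuation.

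**How many subjects**

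Inputs: drug stops for a TEAE in Study 302 Part 1 (Protocol 5.3.1) were 3/41 on 110 mg, 1/40 on 150 mg and 1/39 on placebo. Planned size here is 8 per arm. Assumption: the same rates apply, independently between subjects.

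- Expected number = 8 × 3/41 + 8 × 1/40 + 8 × 1/39 = 0.585 + 0.200 + 0.205 = 0.99.
- P(none) = (38/41)^8 × (39/40)^8 × (38/39)^8 = 0.361, so P(at least one) = 0.64.
- P(exactly one) = 0.361 × (8 × 3/38 + 8 × 1/39 + 8 × 1/38) = 0.361 × 1.047 = 0.378.
- P(two or more) = 1 − 0.361 − 0.378 = 0.26.
- For the 19 subjects dosed by April 2020 (Protocol 5.3.3), pro rata: expected 0.99 × 19/24 = 0.78; P(at least one) = 1 − 0.361^(19/24) = 0.55.

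These count all AE stops of drug. Those that fall under the general trigger, occur before Week 24, and are handled under 14.4 are fewer.

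**The case against.** The strongest reply is that 8.3.2 plainly governs. Section 14.4 is about closing the study or a site. It defers to 8.3 and disclaims other formal stopping rules in the sentence immediately before, and it gives no visit or follow-up instruction that a site could carry out instead. The protocol is also loose elsewhere: 8.3.1 foresees that the reason for a subject's withdrawal may be an AE, and the AE definition in 12.1.1.1 mentions abnormal results that lead to withdrawal from the study. Most of this stands. It makes imprecise drafting the likelier explanation, and nothing in the documents shows that any site acted on 14.4. It does not remove the conflict, because the 14.4 sentence is mandatory and states an action that 8.3 does not contain.

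It also stands that 8.3.2 only requests further visits, so following it does not guarantee the Week 24 score.

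A reader might infer that 14.4 also costs the off-drug diary data needed for the two missing-data sensitivity analyses in SAP 8.6.2. The documents do not support charging that to 14.4 alone. Protocol 11.4 says "Subjects who discontinue study drug should continue to record the occurrence of angioedema events in their e-diary until the follow-up visit", and the list in 10.3.5.3, for a visit about 3 weeks after the last dose, includes "Review and collection of e-diary". The diary can therefore be read as ending then even under 8.3.2.

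**Conclusion.** The inconsistency is real and in current text; its severity is minor. If a site followed 14.4 before Week 24, the loss would be that subject's Week 24 AE-QoL score and completer status. The primary analysis is untouched.

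The size rests on Study 302 rates carrying over: about 1 AE-related drug stop expected among 24 subjects, with a 64% chance of at least one and about 26% of two or more. A reader might take the expected value of about 1 as a ceiling on the count, which it is not. It bounds only the expected number, and does so because some stops fall under the drug-only rules and a site may well follow 8.3.2.

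A reader might also want the number of visits lost per subject. The documents do not fix it: they give no stop times, and the timing of the early termination visit differs between Protocol 7 (within 3 weeks, plus 1 week), 10.1 (3 weeks, plus 1 week) and 10.3.5.3 (approximately 3 weeks).

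**What to change.** In Protocol 14.4, change the action to *discontinued from study drug (see Section 8.3.2)*, or delete the sentence, since 8.3.2 already covers it. This is one phrase in the next amendment and adds no visits, because 8.3.2 already requests them.

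If Parts 1 and 2 are already complete, check for each AE stop which rule the site applied, and report any missing Week 24 AE-QoL score or lost completer status that came from following 14.4. On the figures above, that is about one expected Part 1 subject plus any Part 2 AE stops.
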